## 5. SAMPLE SIZE CALCULATIONS

The primary outcome measure is the difference in OI at day 7, between aspirin and placebo treated groups. Based on our data from a recently completed clinical trial in ARDS, the mean (standard deviation; SD) OI at day 7 in patients with ARDS is 62 (51) cmH2O/kPa. A sample size of 56 subjects (28 in each group) will have 80% power at a two-tailed significance level of 0.05 to detect a clinically significant difference of 39 cmH2O/kPa in OI between groups. In a previous phase 2 study of similar size, we have found that an intervention can demonstrate a change in OI of a similar magnitude confirming a treatment effect of this size can be achieved.

Although we anticipate few withdrawals or loss to follow-up we have allowed for this in the sample size calculation. In our previous single centre study of simvastatin in ARDS there were no withdrawals. In a multi-centre UK study of pulmonary artery catheters in ICU patients

(PAC-Man), no patients were lost to follow up, and only 3% withdrew consent after recovering competency. This is in keeping with our local data. Therefore, a drop-out rate of 5% has been estimated and the study will require a total of 60 patients (30 in each group). All calculations assume 80% power at a two-tailed significance level of 0.05.

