### **2.1 Primary outcome measure**

The primary outcome measures OI at day 7. OI is a physiological index of the severity of ARDS and measures both impaired oxygenation and the amount of mechanical ventilation delivered. We and others have shown OI is independently predictive of mortality in patients with ARDS. We have chosen day 7 as we expect this time interval will minimise the competing effects of death and extubation, while allowing a sufficient time interval for a biological effect to occur.

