### 3.4 Data verification

Data verification, consistency and range checks will have been performed at the data entry stage by the CTU, as well as checks for missing data (copies can be found in the Trial Master File). Additional range, consistency and missing data checks will be performed, as appropriate, when the analysis is performed (and when the datasets for analysis are constructed). All variables will be examined for unusual, outlying, unlabelled or inconsistent values.

Given the thorough nature of our follow-up procedure we expect the issue of missing data to be relatively minimal. We anticipate high compliance with initial data collection as this is close to the time of patient registration. If any data is missing imputation will not be done.

Any problems with trial data will be queried with the Trial Managers, Data Managers, or statisticians, as appropriate. If possible, data queries will be resolved, although it is accepted that due to administrative reasons and data availability a small number of problems will continue to exist. This will be minimised.

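### The 80% power holds only if 28 patients per arm have a measured day-7 OI, and the 5% allowance leaves out death, extubation and ICU discharge

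*SAP*

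**What the plan says.** **Sample size (SAP Section 5).** The endpoint is defined by "The primary outcome measure is the difference in OI at day 7, between aspirin and placebo treated groups". The planning values come from the sponsor's recent ARDS trial: "OI at day 7 in patients with ARDS is 62 (51") cmH2O/kPa. The target is "to detect a clinically significant difference of 39" cmH2O/kPa, and "A sample size of 56 subjects (28 in each group) will have 80% power at a two-tailed significance level of 0.05". The margin follows: "Therefore, a drop-out rate of 5% has been estimated and the study will require a total of 60 patients (30 in each group"). The section presents it as an allowance for withdrawals and loss to follow-up. It is supported by an earlier single-centre study with no withdrawals and a multi-centre ICU study with no loss to follow-up and 3% consent withdrawal. The section closes with "All calculations assume 80% power at a two-tailed significance level of 0.05".

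**Competing events (Section 2.1).** Day 7 was chosen because "we expect this time interval will minimise the competing effects of death and extubation". No rate is given for either event.

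**Measurement (Sections 2.2 and 4).** Daily measurement ends at day 14, ICU discharge or death, whichever is first. OI is calculated from MAP, FiO2 and PaO2.

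**Missing values (Sections 3.4, 6, 7.4 and Table A3).** Section 3.4 says "we expect the issue of missing data to be relatively minimal" and rules out imputation. Section 6 makes the unadjusted independent-samples t-test primary and carries the last value forward only in a secondary analysis. Table A3 has separate rows for observed and carried-forward values. Section 7.4, however, lists the main endpoint as day-7 OI or, failing that, the last OI available before the patient discontinued.

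**The concern.** The 5% allowance and the primary analysis do not describe the same losses. Section 5 counts patients who withdraw or cannot be traced. The primary t-test needs a number for each patient on day 7. A patient can be fully followed, with no withdrawal and no data-entry failure, and still have no day-7 OI because they died, left ICU or no longer needed a ventilator.

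The 80% figure is the one against which a non-significant result will be judged. If it depends on a condition that the SAP does not state, readers cannot tell whether the trial met its own design assumption.

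**Working it through.** **Inputs.** Difference 39 and SD 51 cmH2O/kPa, two-sided alpha 0.05, 28 evaluable and 30 randomised per arm (all Section 5); 1:1 allocation (Section 1).

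**Formula.** For n patients per arm in a two-sample t-test, the noncentrality is δ = 39 / (51 × √(2/n)) on 2n − 2 degrees of freedom. Power is the probability that a noncentral t with these parameters exceeds the two-sided 5% critical value in absolute size. The standardised difference is 39/51 = 0.765.

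**Step 1: reproduce the plan.**
- At n = 28, δ = 39 / (51 × √(2/28)) = 2.86, df = 54, critical value 2.005, power 80.2%. The smallest n for 80% is 27.8, which rounds up to 28. The stated 56 is right.
- 56 / 0.95 = 58.9, so 59, or 60 with equal arms. The stated 60 is right.
- With all 60 evaluable, power is 83.0%.

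**Step 2: find the margin.** 60 − 56 = 4 patients, and 4/60 = 6.7%. This has to absorb every reason for a missing day-7 OI. At 27 per arm power is 78.7%.

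**Step 3: establish who has no day-7 OI.**
- Death or ICU discharge before day 7: measurement has stopped (Section 2.2).
- Off ventilatory support: OI needs MAP. The SAP does not spell out MAP in the formula, but the OI unit is cmH2O/kPa and Table A5 lists mean airway pressure in cmH2O, so MAP is read here as an airway pressure. Without ventilatory support there is none to enter.
- Nothing in the primary analysis restores these patients, because Section 3.4 excludes imputation and Section 6 and Table A3 keep the carried-forward analysis separate.

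**Step 4: show the range.** The SAP gives no rate for these events, so the losses of 10% to 40% below are assumptions. They are totals for all causes, split equally between arms, with n = 30 × (1 − loss). The last column is the difference that gives 80% power at that n with SD 51.

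| Without day-7 OI | Evaluable (per arm) | Power for 39 | Difference detectable at 80% power (cmH2O/kPa) |
|---|---|---|---|
| 5% (the plan's allowance) | 57 (28.5) | 81% | 38.5 |
| 10% | 54 (27) | 78.7% | 39.6 |
| 20% | 48 (24) | 73.7% | 42.1 |
| 30% | 42 (21) | 67.7% | 45.2 |
| 40% | 36 (18) | 60.6% | 49.0 |

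**The case against.** The strongest defence has four parts.

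1. **Nothing in Section 5 is miscalculated.** This stands. A reader might infer a sample-size error, but 56 and 60 both reproduce. The weakness is in what the 5% is taken to cover.

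2. **No shortfall is shown.** This stands too. A reader might infer from the table that the trial is underpowered, but the SAP gives no share of patients without a day-7 OI. At 10% total loss the deficit is 1.3 points (80 − 78.7) and hardly matters. It becomes material from about 20%, and no section shows that 20% is reached. Some patients on non-invasive support, which Section 4 counts as ventilatory support, may still have an OI, so extubation need not always mean a missing value.

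3. **The plan does not overlook death and extubation.** Correct as far as it goes. Section 2.1 gives them as a reason for choosing day 7, and Section 6 plans a carried-forward analysis. Neither enters the power calculation, so this limits the point to Section 5 and does not remove it.

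4. **Section 7.4 would keep most of these patients.** If its last-available definition governed, the number analysed would be largely preserved. But it conflicts with Sections 3.4 and 6 and with Table A3. It would also change the endpoint, and the SD of 51 was obtained for day-7 values.

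A reader might also infer that a null result is bound to be over-read. The SAP commits to estimates with 95% confidence intervals in a phase 2 trial, so the precision achieved will be visible whatever the planned power.

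**Conclusion.** The point holds as a condition missing from the power statement. Section 5's 80% requires 28 patients per arm with a measured day-7 OI. The 5% allowance covers only withdrawal and loss to follow-up, while the primary analysis in Section 6 and Table A3 also loses patients who die, leave ICU or come off ventilatory support before day 7. Once more than 4 of 60 values are missing for all causes combined, the stated power is not delivered.

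How far it falls cannot be determined from the SAP. Over the assumed losses of 10% to 40%, power runs from 79% to 61% and the detectable difference from 39.6 to 49.0 cmH2O/kPa. These figures rest on the SAP's SD of 51 applying to the patients who remain, equal loss in the two arms, the observed-value reading of the primary analysis, and MAP meaning mean airway pressure.

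**What to change.** Keep 60 patients and amend the SAP wording.

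1. **Section 5.** State that 80% power is conditional on 28 patients per arm with an observed day-7 OI, and that death, ICU discharge or coming off ventilatory support before day 7 also removes patients from this analysis. Give power at the share without a day-7 OI in the sponsor's earlier ARDS trial that supplied the mean of 62 and SD of 51. If that share is unavailable, give 79%, 74%, 68% and 61% for total losses of 10%, 20%, 30% and 40%, labelled as assumptions.
2. **Section 7.4.** Reconcile the last-available definition with Sections 3.4 and 6, so that the power statement and the primary analysis refer to the same patients. If the last-available definition is chosen, justify the SD of 51 again for that endpoint.
3. **Section 3.4.** Limit the expectation of minimal missing data to data-collection failures, and say that it does not extend to death, extubation or discharge.

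The cost is SAP text and one look-up in the sponsor's own data. No patients are added. The power statement may become less favourable.

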## 6. ANALYSIS PRINCIPLES

Primary outcome measure is the OI at day 7. Unadjusted (primary analysis) and adjusted analysis will be carried out to test whether there is a statistically significant difference between the aspirin & placebo groups. Secondary analysis will be carried out, if the day 7 OI values are missing, using last value carry forward method.

Secondary outcome measures are OI, CRs, PF ratio, and SOFA score at day 4, 7, 14 and safety. Unadjusted and adjusted analysis will be carried out on OI, CRs, PF ratio, SOFA score, to test whether there is a statistically significant difference between the groups.

Unadjusted analysis will be carried out using Independent sample t-test. Adjusted analysis will be carried out using ANCOVA or [mixed modelling technique](#), based the number of data points available at each time point. Estimates & 95% confidence interval will be reported.

The number of AE, ARs, SAE, SARs, SUSARs and number (%) of patient experiencing the events will be reported. Fisher's exact test and proportion test will be used to check whether incidences of adverse events differ between the groups. Relative risk and 95% CI will be reported.

Exploratory analysis on mediators will be carried out using student t-tests or non-parametric alternative and Fishers Exact Test, presented by day where applicable. The estimates & 95% CIs will be reported. Statistical diagnostic methods will be used to check for violations of the assumptions, and transformations will be performed if required. For binary outcome measures, risk ratios and associated 95% CI will be calculated. Survival analysis technique will be used for time-to-event data. Median survival time & 95% CI will be estimated using Kaplan-Meier estimation method and the Kaplan-Meier plots will be presented. In all time-to-event analyses, patients that did not experience the event in question (e.g. death) were censored on the date last seen or 90 days. The equality of survivorship function of aspirin & placebo group will be tested

for significance using a log-rank  $\chi^2$  test. Hazard ratios (HRs) & 95% CIs will be reported if the proportionality assumption holds.

Correlations between changes in the biological markers measured and physiological and clinical outcomes will be assessed by appropriate graphical and statistical methods including Pearson's (or Spearman's) correlation coefficient.

A secondary analysis excluding patients identified to have aspirin resistance will also be undertaken.

Analyses will be conducted according to intention to treat principle. All statistical tests will be 2-sided and a p-value of 0.05 will be considered as statistically significant, unless adjustment for multiple testing was needed. A single analysis is planned at the end of the trial. Every effort will be made to minimise missing baseline and outcome data in this trial. Any ad-hoc analysis will be reported as per the regulatory requirement.

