### **2.2 Secondary outcome measures**

The following secondary clinical outcomes will also be assessed:

1. OI at days 4 and 14
2. Physiological indices of ARDS, as measured by respiratory compliance (CRs) and P/F ratio on days 4, 7 and 14
3. Organ failure as measured by change in sequential organ failure assessment (SOFA) score from baseline to days 4, 7 and 14
4. Safety and tolerability as assessed by the occurrence of adverse events/reactions (AE/AR), serious adverse events/reactions (SAE/SAR) and suspected unexpected serious adverse reactions (SUSAR).

Outcomes will be measured at baseline and daily up to day 14 or until the patient is discharged from ICU or the patient dies. Although duration of ventilation, ventilation free days at day 28 and 28 and 90-day mortality as well as length of ICU stay will be recorded, these important clinical outcomes are not included as major outcome measures as the study is not adequately powered to assess these outcomes.

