### **7.2 Baseline Characteristics**

The randomisation is stratified by vasopressor requirement. Refer to table A1. Baseline characteristics at trial entry

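### The primary analysis of day-7 OI is a valid but unadjusted t-test, which gives up precision that baseline OI and the vasopressor stratum could supply

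*SAP*

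**What the plan says.** SAP section 6 plans two comparisons of OI at day 7 and ranks them: "Unadjusted (primary analysis) and adjusted analysis will be carried out to test whether there is a statistically significant difference". It then fixes the first: "Unadjusted analysis will be carried out using Independent sample t-test". The second is left open: "Adjusted analysis will be carried out using ANCOVA or" a mixed model, the choice being "based the number of data points available at each time point". No covariate is named for the adjusted analysis, in section 6 or in the table shells.

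Two candidate covariates are available. Section 2.2 says "Outcomes will be measured at baseline and daily up to day 14", and Tables A1 and A3 both have a row for baseline OI. Section 7.2 says "The randomisation is stratified by vasopressor requirement", and Table A1 reports that factor.

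Section 5 sizes the trial on the raw scale without adjustment. It takes a day-7 mean of 62 and SD of 51 cmH2O/kPa, 28 evaluable patients per group, 80% power and two-sided 0.05, "to detect a clinically significant difference of 39" units.

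**The concern.** Stratified randomisation balances the stratum between arms, so a prognostic stratum contributes less to the true variability of the treatment difference than its share of the outcome variance suggests. A two-sample t-test still counts that share as noise. Its standard error is then too large, its interval too wide and its actual type I error below 5%.

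Baseline OI is not balanced by design. With 28 to 30 patients per arm some imbalance is expected, and it passes into the unadjusted difference in proportion to the correlation between baseline and day 7.

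What is at stake is precision in a 60-patient trial. A secondary consequence is that Table A3 prints an adjusted p-value beside the unadjusted one for the primary outcome, while the model behind it has neither named covariates nor a fixed method.

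**Working it through.** **Inputs from SAP section 5:** difference 39, SD 51, 28 per arm, two-sided 0.05, dropout 5%. **Not in the SAP, so assumed:** correlation r between baseline and day-7 OI, 0.2 to 0.6; share R² of day-7 variance explained by the vasopressor stratum, 0.05 to 0.30.

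**1. Reproduce the plan.** SE = 51 × √(2/28) = 13.63. Noncentrality = 39/13.63 = 2.86 on 54 df. Power by noncentral t is 0.802 at 28 per arm and 0.787 at 27, so 28 per arm is right. Then 56/0.95 = 58.9, that is 59, rounded up to an even 60. The sample size and the primary test agree with each other.

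**2. Add baseline OI.** Residual SD = 51 × √(1 − r²), with one further df lost. Half-width = t(0.975, df) × residual SD × √(2/28).

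| r | Residual SD | Power for 39 units, 28 per arm | 95% CI half-width | Per arm for 80% power |
|---|---|---|---|---|
| none (t-test) | 51.0 | 0.802 | 27.3 | 28 |
| 0.2 | 50.0 | 0.818 | 26.8 | 27 |
| 0.3 | 48.7 | 0.838 | 26.1 | 26 |
| 0.4 | 46.7 | 0.865 | 25.1 | 24 |
| 0.5 | 44.2 | 0.900 | 23.7 | 22 |
| 0.6 | 40.8 | 0.940 | 21.9 | 19 |

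These figures are slightly favourable to ANCOVA. Estimating the slope adds about 1/(2n − 4) = 1/52, or 2%, to the expected variance, which matters only at the lowest correlations.

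**3. Size of the chance imbalance.** The standardised baseline difference between arms has SD √(2/28) = 0.267. An imbalance of that size moves the unadjusted estimate by r × 0.267 × 51: 2.7 units at r = 0.2, 6.8 at 0.5 and 8.2 at 0.6.

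**4. Leave out the stratum.** With exact balance within strata the true SE is 13.63 × √(1 − R²): 12.93 at R² = 0.10 and 12.19 at 0.20. The t-test goes on using about 13.63. Simulation (40,000 runs, 56 patients, two equal strata) gives:

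| R² | Type I error, t-test | Type I error, stratum in model | Power at 39, t-test | Power at 39, stratum in model |
|---|---|---|---|---|
| 0.05 | 0.046 | 0.051 | 0.803 | 0.817 |
| 0.10 | 0.039 | 0.050 | 0.813 | 0.842 |
| 0.20 | 0.028 | 0.050 | 0.826 | 0.881 |
| 0.30 | 0.018 | 0.049 | 0.843 | 0.920 |

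**5. Scale.** OI cannot be negative, yet a normal curve with mean 62 and SD 51 puts P(Z < −62/51) = P(Z < −1.216) = 11.2% below zero. The planning figures therefore imply right skew.

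**The case against.** The case for leaving the plan alone is serious. In a 1:1 randomised trial the t-test estimates the mean difference without bias. Omitting a balanced stratum errs on the safe side. The sample size was worked out for exactly this test and holds up. Adjusted estimates, intervals and p-values are planned and shown in Table A3. The size of any gain rests on a correlation and an R² that the SAP does not give; at r of 0.2 to 0.3 power rises only to 0.82 to 0.84. All of this stands, and it rules out calling the primary analysis wrong.

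What does not stand is that the planned adjusted analysis already covers the point. It is not primary, it names neither baseline OI nor the stratum, and its method is to be settled by how much data there is at each time point.

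Three stronger readings should be resisted:

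- **That standard errors ignoring the stratification produce false positives.** Step 4 shows the reverse.
- **That skew leaves the trial underpowered.** A lognormal simulation with mean 62, SD 51 and r = 0.5 gives about 65% power for the raw t-test, about 73–74% for raw ANCOVA and 85% for log ANCOVA. That is for a 40% reduction, or 0.40 × 62 = 24.8 units. The plan is for 39 units, or 39/62 = 63%; there all three methods reach about 99% or more under the same model. The 65% describes a smaller effect and is not a shortfall against the plan.
- **That the log scale is required.** It replaces the mean difference powered in section 5 with a ratio of geometric means, so it is a different estimand. Section 6 also allows transformation after diagnostics, although it is unclear whether that sentence reaches beyond the exploratory mediators.

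**Conclusion.** The point holds as a matter of efficiency. The primary t-test is valid, conservative if the stratum is prognostic, and consistent with the stated 80% power. Adjusting for baseline OI would raise power for 39 units from 0.80 to between 0.82 and 0.94, and cut the expected CI half-width from 27.3 to between 26.8 and 21.9, if the baseline-to-day-7 correlation is between 0.2 and 0.6. Including the stratum would bring type I error back to about 5% and add power according to how prognostic it is. The direction of the gain is secure if either covariate is prognostic; its size depends on figures that the SAP does not give. The gap that needs no assumption is that the adjusted model's covariates and method are not fixed in advance.

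**What to change.** In section 6:

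- Make the primary analysis of day-7 OI an ANCOVA with treatment, baseline OI and vasopressor stratum as the pre-specified terms. It still estimates a mean difference in cmH2O/kPa, so the 39-unit target keeps its meaning.
- Keep the independent-sample t-test as a supportive analysis.
- Replace the choice between ANCOVA and mixed model with this fixed model. If the mixed model in Table A4 is kept, list it as a separate supportive analysis with its terms stated.
- Optionally, add a pre-specified sensitivity analysis on log OI, reported as a ratio of geometric means and labelled as a different estimand.

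Relabel Table A3 to show which comparison is primary. The sample size in section 5 can stay, since the unadjusted SD of 51 is the cautious choice if baseline OI or the stratum is prognostic. If power under skew is quoted anywhere, state the effect size beside it.

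The cost is SAP wording and table labels. Both covariates are already in Table A1, so no patients, visits or data items are added. The change should be made before anyone sees outcome data by arm.

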# 1. BACKGROUND AND DESIGN

The trial hypothesis under investigation is that treatment with aspirin is safe and improves important surrogate clinical outcomes in adult patients with ARDS.

The objective of the trial is

1. To conduct a prospective randomised, double-blind, allocation concealed, placebo-controlled phase 2 trial of aspirin as a treatment for ARDS.
2. To study the biological effects of aspirin on pulmonary and systemic
  - a. inflammatory responses,
  - b. epithelial and endothelial function and injury and
  - c. lipid inflammatory mediators

Subjects will be randomised to receive aspirin 75mg capsule or a placebo capsule enterally for up to 14 days. Subjects will be randomised in a 1:1 ratio using blocks of variable size. The first dose of the study drug will ideally be administered within 4 hours of randomisation and subsequent doses will be as close to 10 am as possible starting on the following calendar day.

Patients will be eligible to participate in the study if they fulfil the following criteria:

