Lowest eGFR mL/min									
	Aspirin	n	xx.x ± x.x	n	xx.x ± x.x	n	xx.x ± x.x	n	xx.x ± x.x
	Placebo	n	xx.x ± x.x	n	xx.x ± x.x	n	xx.x ± x.x	n	xx.x ± x.x
	p-value #			0.xxx		0.xxx		0.xxx	

# p values for ANCOVA or mixed model

**Table A 2.. Adverse events/reactions (AE/AR), serious adverse events/reactions (SAE/SAR) & suspected unexpected serious adverse reactions**

		Number of Events			Number of Patients				
		Total	Aspirin	Placebo	Total N=<n>	Aspirin N=<n>	Placebo N=<n>	RR (95%I)	p-values
AE/AR, SAE/SAR and SUSAR	Total number of adverse events (AEs)	n	n	n	n (%)	n (%)	n (%)	x.xx (x.xx to x.xx)	x.xx
	Total number of adverse reactions (ARs)	n	n	n	n (%)	n (%)	n (%)	x.xx (x.xx to x.xx)	x.xx
	Total number of serious adverse events (SAEs)	n	n	n	n (%)	n (%)	n (%)	x.xx (x.xx to x.xx)	x.xx
	Total number of serious adverse reactions (SARs)	n	n	n	n (%)	n (%)	n (%)	x.xx (x.xx to x.xx)	x.xx
	Total number of events related to study drug and unexpected (SUSAR)	n	n	n	n (%)	n (%)	n (%)	x.xx (x.xx to x.xx)	x.xx
AEs	Blood and lymphatic system disorders	n	n	n	n (%)	n (%)	n (%)	x.xx (x.xx to x.xx)	x.xx
	Cardiac disorders	n	n	n	n (%)	n (%)	n (%)	x.xx (x.xx to x.xx)	x.xx
	Gastrointestinal disorders	n	n	n	n (%)	n (%)	n (%)	x.xx (x.xx to x.xx)	x.xx
	Hepatobiliary disorders	n	n	n	n (%)	n (%)	n (%)	x.xx (x.xx to x.xx)	x.xx
	General disorders and administration site conditions	n	n	n	n (%)	n (%)	n (%)	x.xx (x.xx to x.xx)	x.xx
	Infections and infestations	n	n	n	n (%)	n (%)	n (%)	x.xx (x.xx to x.xx)	x.xx
	Injury, poisoning and procedural complications	n	n	n	n (%)	n (%)	n (%)	x.xx (x.xx to x.xx)	x.xx
	Musculoskeletal and connective tissue disorders/Elevated Creatinine Kinase	n	n	n	n (%)	n (%)	n (%)	x.xx (x.xx to x.xx)	x.xx
	Investigations	n	n	n	n (%)	n (%)	n (%)	x.xx (x.xx to x.xx)	x.xx
	Nervous system disorders	n	n	n	n (%)	n (%)	n (%)	x.xx (x.xx to x.xx)	x.xx
	Renal and urinary disorders	n	n	n	n (%)	n (%)	n (%)	x.xx (x.xx to x.xx)	x.xx
	Respiratory, thoracic and mediastinal disorders	n	n	n	n (%)	n (%)	n (%)	x.xx (x.xx to x.xx)	x.xx
Skin and subcutaneous tissue disorders	n	n	n	n (%)	n (%)	n (%)	x.xx (x.xx to x.xx)	x.xx	
SAEs	Blood and lymphatic system disorders	n	n	n	n (%)	n (%)	n (%)	x.xx (x.xx to x.xx)	x.xx
	Cardiac disorders	n	n	n	n (%)	n (%)	n (%)	x.xx (x.xx to x.xx)	x.xx
	Gastrointestinal disorders	n	n	n	n (%)	n (%)	n (%)	x.xx (x.xx to x.xx)	x.xx
	Hepatobiliary disorders	n	n	n	n (%)	n (%)	n (%)	x.xx (x.xx to x.xx)	x.xx

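### Relative risk is the only between-group effect measure planned for harms, so rows with no placebo events carry no usable upper limit on excess risk

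*SAP*

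**What the plan says.** SAP section 6 (Analysis Principles) plans these outputs for harms:

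- Description: "The number of AE, ARs, SAE, SARs, SUSARs and number (%) of patient experiencing the events will be reported".
- Tests: "Fisher's exact test and proportion test will be used to check whether incidences of adverse events differ between the groups".
- Effect measure: "Relative risk and 95% CI will be reported".

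The general rule later in the same section uses the same scale: "For binary outcome measures, risk ratios and associated 95% CI will be calculated".

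The adverse-event table in Appendix 1 follows this layout. Each row has event counts, patients with n (%) in total and by arm, one relative-risk column with its interval, and a p-value. There are 31 rows: 5 totals (including the row "Total number of events related to study drug and unexpected (SUSAR")), 13 organ classes for adverse events and 13 for serious adverse events. Neither section 6 nor the table has a risk difference, a named interval method or a rule for a cell with no events. Section 7.5 adds only numbers and percentages by arm.

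**The concern.** The organ-class, SAR and SUSAR rows divide about 30 patients per arm into small cells, and the ratio has the placebo proportion in its denominator. The scale therefore breaks down where events occur on aspirin and none on placebo, a pattern that a safety review would want to size.

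Section 1 makes safety part of the trial hypothesis, and section 2.2 lists it as a secondary outcome. A statement about safety needs an upper limit on how much extra risk the data allow. In a row with no placebo events, the planned effect measure supplies no such limit, or supplies one that depends on a correction chosen after the data are seen.

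**Working it through.** **Inputs.** Section 5 gives 30 patients per arm, and section 1 gives 1:1 allocation. Event risks are not in the SAP, so they are assumed over a range.

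**The plan's own figure.** For a difference of 39 with SD 51, two-sided 0.05 and 80% power, the noncentral t calculation gives 27.84, so 28 per arm (power 80.2%). Then 56/0.95 = 58.9, so 59, or 60 with equal arms. The SAP's 56 and 60 reproduce. There is no SAP figure for harms to reproduce.

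**1. How often a row has no placebo events.** Let q = P(0 of 30) = (1 − p)^30.

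| Assumed true placebo risk p | q: no placebo events | Exactly one arm empty, equal risks: 2q(1 − q) | Both arms empty, equal risks: q² | Aspirin events but none on placebo, aspirin risk 2p: q[1 − (1 − 2p)^30] |
|---|---|---|---|---|
| 1% | 74% | 39% | 55% | 34% |
| 2% | 55% | 50% | 30% | 39% |
| 3% | 40% | 48% | 16% | 34% |
| 5% | 21% | 34% | 5% | 21% |
| 10% | 4% | 8% | 0.2% | 4% |

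**2. What the relative risk gives at a/30 v 0/30.**

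- Estimate: (a/30)/(0/30), which is not finite.
- Log-Wald variance: 1/a − 1/30 + 1/0 − 1/30, which is undefined, so there is no interval.
- Score (Koopman) interval: a lower limit only. It is 1.11 at 4 v 0 and 1.69 at 6 v 0, with an infinite upper limit.
- Adding 0.5 to each cell: RR = (a + 0.5)/0.5 and SE(log RR) = √[1/(a + 0.5) − 1/30.5 + 1/0.5 − 1/30.5]. At 6 v 0, RR = 6.5/0.5 = 13.0 and SE = √(0.1538 − 0.0328 + 2 − 0.0328) = 1.445. The interval is 13.0 × exp(±1.96 × 1.445) = 0.77 to 221.

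**3. The same rows on the difference scale, beside the planned test.**

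| Aspirin v placebo (of 30 each) | Fisher p | RR with 0.5 added (95% CI) | Risk difference, points (Newcombe 95% CI) |
|---|---|---|---|
| 1 v 0 | 1.00 | 3.0 (0.13 to 71) | 3.3 (−8.3 to 16.7) |
| 3 v 0 | 0.24 | 7.0 (0.38 to 130) | 10.0 (−3.1 to 25.6) |
| 4 v 0 | 0.11 | 9.0 (0.51 to 160) | 13.3 (−0.6 to 29.7) |
| 5 v 0 | 0.052 | 11.0 (0.64 to 190) | 16.7 (2.0 to 33.6) |
| 6 v 0 | 0.024 | 13.0 (0.77 to 221) | 20.0 (4.5 to 37.3) |

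At 6 v 0 the planned test is significant while the corrected ratio interval includes 1. The difference has a finite estimate and both limits in every row. At 0 v 0 it still bounds the difference at ±11.4 points, where the ratio is 0/0.

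**The case against.** **Harms are not reported only as a ratio.** A reader might infer that a harm seen only on aspirin would go unreported. The SAP does not support that. A 4 v 0 pattern would be printed as 4 (13.3%) v 0 (0.0%) with a p-value, and anyone could compute the difference and its interval from those counts. This stands: what is missing is a planned interval for the difference, not the data.

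**A ratio interval can exist with an empty cell.** A reader might also infer that no interval is possible. That is true only of log-Wald, and the SAP names no method. A score interval has a finite lower limit when placebo is empty. When aspirin is empty it is finite on both sides: 0 to 0.90 at 0 v 4. This also stands, but when placebo is empty the score upper limit is infinite, and the upper limit is the one needed for safety.

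**The frequency is assumed.** At 10% risk an empty placebo row has probability 4%, so overall totals and common organ classes are unlikely to be affected. Counting every row with at least one empty arm would overstate the problem, because it includes rows where nothing happened in either arm (55% of rows at 1% risk). The point is therefore confined to uncommon harms.

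**The proportion test might imply a difference.** Section 6 uses it only to test whether incidences differ, and the table has no column for a difference.

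**The tables are example drafts and the ratio is a conventional choice.** Both are true. A column can be added easily, and the SAP does not contradict itself here. But section 6 itself names only the ratio, so the gap is not confined to the table layout.

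**Conclusion.** The concern holds in this form: the relative risk is the only between-group effect measure planned for harms, with no interval method and no zero-cell rule. In rows with no placebo events it yields no finite estimate, and no finite upper limit without an arbitrary correction. Counts, percentages by arm and a p-value remain.

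At 30 per arm, an empty placebo row has probability 74% to 21% for true placebo risks of 1% to 5%, and 4% at 10%. If aspirin doubled the risk, aspirin events with none on placebo would occur in 34%, 39%, 34% and 21% of rows at placebo risks of 1%, 2%, 3% and 5%. These figures rest on assumed risks and on all 30 patients per arm being counted.

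The primary analysis and the sample size are unaffected. This is a point about statistical reporting and touches no clinical management rule.

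**What to change.** In section 6 and the Appendix 1 adverse-event table, add for every row the risk difference (aspirin minus placebo) with a 95% interval by one method named in advance, for example Newcombe. Show the relative risk beside it only where both arms have events, and name its interval method too.

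The difference method must be a single choice. At 4 v 0 the Newcombe interval includes zero (−0.6 to 29.7 points). A Miettinen-Nurminen interval would exclude it: the statistic at no difference is (4/30)² / [2 × (4/60)(56/60)/30 × 60/59] = 4.21, against a critical value of 3.84.

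State that the interval is for estimation, because it can disagree with Fisher's test at the margin. At 5 v 0 the Newcombe interval is 2.0 to 33.6 points while Fisher's p is 0.052.

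The cost is a few sentences in section 6 and one more table column, with no new data. Risk differences also transfer less readily to populations with other baseline risks, which is a reason to keep the ratio where it can be estimated.
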